NICU practice guidelines for hypoglycemia monitoring vary from institution to institution. Often, blood glucose testing is done only prior to feeds, which leaves these infants vulnerable to undetected hypoglycemia. Even with frequent blood sampling using bedside glucometers there can be a delay in recognition and treatment of hypoglycemia. CGMs measure glucose concentration in the interstitial fluid of the subcutaneous space every few seconds and report average blood glucose levels approximately every 5 minutes. CGMs have 3 components: a glucose sensor, a transmitter, and a receiver. The glucose sensor is inserted subcutaneously with a 26-gauge introducer needle and remains in place under the surface of the skin for up to 7 days. The sensor's platinum tip is embedded with glucose oxidase enzyme, which catalyzed a reaction whereby electrical current is generated which is proportional to ambient glucose concentration. The current is then measured and translated into a glucose reading once it is wirelessly sent by the transmitter to the small hand-held receiver. The receiver then displays the glucose level in mg/dL and can alert at specified glucose levels. CGMs are inserted with minimal discomfort and no significant complications have been reported when they are used in children less than 3 years of age (8). CGMs are considered by IRBs to be non-significant-risk devices because they are not considered implants, they are placed only subcutaneously, they are completely removed within 7 days, and they do not offer treatment for or diagnosis of a medical condition. In our study, no clinical decision or intervention will be made based on the CGM readings. Instead, the CGMs will function as monitoring systems that will prompt FDA-approved glucose meter measurements, and only on these blood-based results will clinical care be based.

Although CGMs are increasingly being used in the diabetic population, their efficacy has not been investigated in the management of neonatal hypoglycemia. However, their use in the neonatal population, including in very-low-birth-weight infants, has been validated. Studies report that the sensor is well tolerated and provides readings comparable to those of whole blood results (9). It has also been shown that currently in a typical NICU, there are often prolonged periods (up to 12 hours) between blood glucose measurements, and that with CGMs, hypoglycemia is detected up to 3 hours prior to the scheduled blood glucose test (9).

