Infants will be randomized to a "CGM Protocol" or a "Standard of Care" group. We aim to enroll ten patients in each study arm. Those on the CGM Protocol will have a fully accessible CGM that will be analyzed in real-time for blood glucose trends and will alarm for any blood glucose level approaching hypoglycemic threshold. The CGM alarm will sound if blood glucose is less than 60 mg/dL for all patients. The CGM will also alarm if the rate of drop in blood glucose is greater than 20 mg/dL/minute and thus concerning for impending hypoglycemia. These thresholds are programmed into the CGM by a study team member and will not be modifiable by the medical team. Those in the "Standard of Care" group will have a CGM in place but live readings will not be available to the clinical team. However, the research team will review CGM data from the "Standard of Care" group daily and if a subject in the "Standard of Care" group has three episodes of unrecognized severe hypoglycemia (eg. BG <40 mg/dL), the study team will alert the NICU providers. Notification will occur immediately following identification of the third unrecognized severe episode of hypoglycemia, which will at most be 24 hours after the event occurred.

For subjects in the "CGM Protocol" group, whenever the CGM alarms or there is a concerning blood glucose trend according to the CGM, the nurse will be asked to check a blood glucose value. All clinical

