- *Assessments:*

The CGM site will be evaluated daily to assess for any signs of bleeding or infection. CGM readings will be downloaded to a study team computer once a day. The CGM data will be reviewed daily to ensure the CGM monitor is functioning properly, being calibrated appropriately and to assess whether any episodes of severe unrecognized hypoglycemia have occurred.

- *Interventions:*

Subjects in the study will have a continuous glucose monitor (CGM) placed in one of their thighs. A numbing cream will be used before the CGM is inserted to reduce pain. The CGM has a small plastic catheter with a needle in it. It comes with an insertion device which pushes the catheter under the skin. The needle is then removed, so only the catheter stays under the skin with the device on top of it. After the CGM is placed, two blood glucose levels will be obtained (usually by heel prick) so that the device can be calibrated. Afterwards at least two blood sugar levels need to be obtained every day so that the CGM can continue to work properly. Infants with hypoglycemia need to have their blood glucose monitored routinely, so on most days no extra blood glucose sampling will be required as we will use the values obtained by the NICU team. Additional blood glucose levels may need to be obtained if the CGM reports current or impending hypoglycemia. All non-CGM monitoring and management decisions will be at the discretion of the NICU team. The CGM may need to be replaced in case of a sensor dislodgement or malfunction, or if it has been in place for more than 7 days. Live CGM glucose values will be available to the medical team in the “CGM protocol” group. Additionally the medical team will be provided print outs of the CGM data on a daily basis for the “CGM protocol” group. CGM data from patients in the “Standard of Care” group will also be reviewed daily. Notification will occur immediately following identification of three unrecognized severe episodes of hypoglycemia. Given that the CGM data will be analyzed daily, this will at most be 24 hours (although most likely less than 24 hours) after the event occurred.

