## 8. Data Analysis Plan

Hypoglycemia will be defined as a laboratory or bedside monitor blood glucose value of <50 mg/dL prior to 48 hours of life and <70 mg/dL after 48 hours of life or CGM values below threshold for >30 minutes with no concomitant blood sugar reading. Hypoglycemic episodes within one hour of each other will be considered as one event. Severe hypoglycemia will be defined as less than 40mg/dL. Euglycemia will be defined as 48 hours with blood glucose equal or greater than 70mg/dL after 48 hours of life or equal or greater than 50mg/dL if before 48 hours of life.

We will record all blood glucose levels, laboratory data related to the investigation of the underlying cause of hypoglycemia, intravenous and enteral sources of glucose, and other related therapeutic interventions such as administration of diazoxide, octreotide, glucocorticoids, and carnitine. Data analysis will begin by comparing blood glucose data with information from the CGM monitors to assess for accuracy of the CGMs. This will be done by calculating the mean-absolute-relative-difference (MARD) between sensor-measured glucose levels and laboratory or bedside meter-measured blood glucose values. We will then compare the severity and frequency of hypoglycemia, as well as the time to diagnosis and time to euglycemia on a sustainable feeding regimen between the “CGM Protocol” and “Standard of Care” groups. Chi-squared analysis will be used to assess differences in the incidence of hypoglycemia while the Mann-Whitney U test will be used to analyze differences in time-to-diagnosis and time-to-euglycemia.

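### Section 8 scores an unchecked sensor low as hypoglycemia but gives euglycemia no sensor condition, so one 48-hour window can satisfy both definitions, more readily in the masked arm

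*Combined protocol and SAP*

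**What the plan says.** Section 8 defines hypoglycemia in two limbs. The blood limb reads "Hypoglycemia will be defined as a laboratory or bedside monitor blood glucose value of <50 mg/dL prior to 48 hours of life", with a limit of 70 mg/dL after that age. The sensor limb adds "or CGM values below threshold for >30 minutes with no concomitant blood sugar reading". Euglycemia has one limb: "Euglycemia will be defined as 48 hours with blood glucose equal or greater than 70mg/dL after 48 hours of life", or at least 50 mg/dL before that age. That sentence does not mention the CGM, does not require the absence of hypoglycemic events and sets no minimum number of readings. No other section defines euglycemia.

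Time-to-euglycemia under sustainable feeding is a secondary outcome (Section 4c). Section 8 compares it between arms by the Mann-Whitney U test.

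Blood sampling differs by arm. In the CGM Protocol arm a sensor warning leads to a bedside check of glucose: "whenever the CGM alarms or there is a concerning blood glucose trend according to the CGM, the nurse will be asked to check a blood" … (Section 4a). In Standard of Care the live trace is hidden from the clinical team, and the study team alerts them only after three unrecognized severe episodes (below 40 mg/dL). The floor on blood sampling in both arms is the calibration requirement: "Afterwards at least two blood sugar levels need to be obtained every day so that the CGM can continue to work properly" (Section 4d, Interventions). Section 4a puts it as at least every 12 hours.

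**The concern.** Hypoglycemia and euglycemia should be mutually exclusive within a window, and as written they are not. A sensor low that nobody checks counts as an event for the primary outcome but does not interrupt the 48-hour run for the secondary outcome.

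Whether a low is checked depends on the arm. In the CGM Protocol arm, a low that alarms leads to a blood check; if confirmed, it becomes a low blood value and breaks the run. In Standard of Care the same low usually stays on the masked trace and the run continues. The arm in which lows go unseen can therefore appear to recover sooner, against the hypothesis for aim (c) in Section 1. Section 1 says the pilot is meant to assess the validity of its outcome measures and to inform a larger trial, so a faulty definition could carry forward.

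**Working it through.** The plan states no figure on this point to reproduce: the 10 infants per arm are a convention, and Section 9 says the study is not powered. The check has three parts.

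**1. Apply both definitions to one constructed record.** Take an infant older than 48 hours of life, so the threshold is 70 mg/dL.
- Blood values: 85 mg/dL at 0, 12, 24, 36 and 48 h, the protocol minimum.
- Sensor: 62 mg/dL for 40 minutes from hour 15, otherwise 85 mg/dL, with no blood reading during the low.
- Hypoglycemia: 40 > 30 minutes, below 70, no concomitant reading, so one event is scored.
- Euglycemia: all five blood values are at least 70, so it is met.

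Both definitions hold in the same 48 hours. If euglycemia also required no event of either limb, this record would fail it.

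**2. Chance that a single low contains no scheduled blood reading.** For a low of D minutes at a random time and readings every I minutes, the chance is 1 − D/I. Only the 12-hourly interval comes from the protocol; the denser schedules and the durations are assumed.

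| Interval | D = 35 min | D = 60 min | D = 120 min |
|---|---|---|---|
| 12-hourly (I = 720) | 95% | 92% | 83% |
| 6-hourly (I = 360) | 90% | 83% | 67% |
| 3-hourly (I = 180) | 81% | 67% | 33% |

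**3. Chance that a 48-hour window shows no low blood value.** Assume L minutes low per day, n blood readings in 48 hours at independent random times, and that a reading taken during a low is itself low. The chance is (1 − L/1440)^n. Two readings a day give n = 4; 3-hourly readings give n = 16. By comparison, one sensor value about every 5 minutes gives 48 × 12 = 576 in the window.

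| L (assumed) | n = 4 | n = 16 |
|---|---|---|
| 45 min/day | 0.96875^4 = 88% | 0.96875^16 = 60% |
| 90 min/day | 0.9375^4 = 77% | 0.9375^16 = 36% |
| 180 min/day | 0.875^4 = 59% | 0.875^16 = 12% |

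Counting readings at both ends of the window (n = 5) gives 0.9375^5 = 72% in place of 77%. If the 90 minutes come as two 45-minute lows, each exceeds 30 minutes, so each one without a concomitant blood reading is a scored event.

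**Limit on the arm contrast.** The level alarm is set at 60 mg/dL for all patients (Section 4a), while the event threshold after 48 hours of life is 70 mg/dL. Sensor values of 60–69 mg/dL at that age trigger no level alarm. The rate alarm needs a fall above 20 mg/dL per minute, which is 5 × 20 = 100 mg/dL over one 5-minute reporting interval. Only a check for a concerning trend remains. The constructed record, at 62 mg/dL, could therefore arise in either arm.

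**The case against.** The strongest objection is that the euglycemia sentence does not exclude the sensor. The protocol elsewhere uses blood glucose loosely for sensor output: Section 2 says CGMs "report average blood glucose levels approximately every 5 minutes", and the alarm rule in Section 4a uses the same term. When Section 8 means blood only, in the hypoglycemia definition, it specifies laboratory or bedside monitor; the euglycemia sentence drops that qualifier. This stands in part: the intended source is arguable. It does not remove the problem. Section 8 itself treats the two as separate sources, for instance in "comparing blood glucose data with information from the CGM monitors". Even on the loose reading the 30-minute rule is not carried over, so a brief dip could end euglycemia without being a hypoglycemic event.

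Second, the illustrative figures use the sampling floor, assumed low time and random timing. Section 2 says testing is often tied to feeds, Section 4a foresees more frequent checks, and sensor accuracy has yet to be assessed by MARD. All of this stands, and it limits what can be said about size.

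Third, the endpoint also requires sustainable feeding, so 48 hours of normal blood values are not sufficient. That may dilute the bias, but it adds no sensor condition.

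A reader might go further and infer that nearly every low in the CGM Protocol arm is caught, so that 77% should be set against zero. The documents do not support this, because of the 60–69 mg/dL gap and because not every alarm need be confirmed by blood. Nor do they support the inference that the trial will show slower euglycemia on CGM from the definitions alone: alarm-prompted sampling in one arm contributes, and any true effect of CGM also enters the observed difference.

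**Conclusion.** The inconsistency holds on the text: as written, a 48-hour window can contain a scored hypoglycemic event and still count as euglycemia. Because blood checks are prompted by alarms in one arm only, ascertainment of time-to-euglycemia differs by arm, and the measurement bias tends toward a shorter time in Standard of Care. The size is unknown. It depends on actual blood sampling and on how often lows occur, and the unalarmed 60–69 mg/dL range partly offsets it. The 77% and 36% illustrate how easily scheduled sampling can miss lows under the stated assumptions; they do not estimate the bias in time-to-euglycemia. This affects a secondary outcome in an unpowered pilot, and it should be corrected because the pilot is meant to test its outcome measures.

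**What to change.** In Section 8, define euglycemia for the endpoint as the first 48 consecutive hours with no hypoglycemic event under that section's definition, on either limb. State that blood and CGM data are both used in both arms, and that any below-threshold blood value, including an alarm-prompted one, breaks the run. Leave the feeding condition as it is. Exempting alarm-prompted values would not work: together with the no-concomitant-reading clause, it could leave blood-confirmed lows uncounted in the CGM Protocol arm.

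Prompted checks would still differ by arm. Add a sensitivity analysis that scores the 48-hour run from the CGM trace alone, with the same rule of more than 30 minutes in both arms and without the no-concomitant-reading clause.

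The cost is a few sentences in Section 8 and one further analysis; the CGM data are already downloaded daily in both arms. Reported times to euglycemia will lengthen, probably more in Standard of Care, and some sensor-only lows may be false, so the results should be read alongside the planned MARD assessment. The change concerns the analysis definition only and alters no care.

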**1. Specific Aims and Objectives**

We seek to improve the management and outcome of neonates diagnosed with hypoglycemia. We hope to accomplish this by using continuous glucose monitors (CGMs) in at-risk infants admitted to the neonatal intensive care unit (NICU). Current management of neonatal hypoglycemia involves intermittent blood sampling, which, unlike CGMs, does not offer real-time blood glucose trends and therefore leaves infants at risk for unrecognized hypoglycemia. Unrecognized hypoglycemia may not only lengthen time to diagnosis and appropriate treatment, but may also lead to poor neurodevelopmental outcomes. Our long-term goal is to assess whether use of CGMs can improve clinical course and outcomes in this population. This pilot study will allow us to test whether it is feasible to perform in larger-scale the proposed randomized, controlled trial comparing a “CGM Protocol” group and a “Standard of Care” group to assess whether use of CGMs in neonates can:

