**a) Reduce the number and severity of hypoglycemic events**

*Hypothesis: Use of CGMs will provide real-time blood glucose trends, allowing hypoglycemia to be predicted and prevented, or detected and treated before becoming severe or symptomatic.*

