#### ***Description of Study Treatments or Exposures/Predictors***

Continuous Glucose Monitors (CGMs) will be placed in all enrolled patients. CGMs measure glucose concentration in the interstitial fluid of the subcutaneous space every few seconds and report average blood glucose levels approximately every 5 minutes. CGMs have 3 components: a glucose sensor, a transmitter, and a receiver. The glucose sensor is inserted subcutaneously with a 26-gauge introducer needle and remains in place under the surface of the skin for up to 7 days. The sensor’s platinum tip is embedded with glucose oxidase enzyme, which catalyzed a reaction whereby electrical current is generated which is proportional to ambient glucose concentration. The current is then measured and translated into a glucose reading once it is wirelessly sent by the transmitter to the small hand-held receiver. The receiver then displays the glucose level in mg/dL and can alert at specified glucose levels.

*c. Definition of Primary and Secondary Outcomes*

This is a pilot study to determine the feasibility of using CGMs to improve short term outcomes of neonates with hypoglycemia. Planned comparisons for a larger study will be powered from the data obtained. The primary endpoint will be a reduction in incidence and severity of hypoglycemia in infants on the CGM Protocol. Secondary outcomes will include reduction in in time-to-diagnosis, time-to-treatment initiation and time-to-euglycemia on a sustainable feeding regimen.

*d. Data Collection Methods, Assessments and Interventions*

- *Data collection:*

When a subject is first enrolled we will collect demographic Information (age at diagnosis of hypoglycemia, gestational age at birth, sex) as well as physical characteristics (weight and body surface area). Once a subject is on a CGM, the CGM glucose data will be downloaded onto a research team computer and reviewed daily. Laboratory results (including blood glucose levels and critical sample results (ketones, insulin, cortisol, growth hormone, fatty acids, total and free carnitine, plasma amino acids, urine organic acids, lactic acid, pyruvate), brain imaging and EEG readings, all intravenous and enteral sources of glucose, other sources of nutrition, hypoglycemia therapeutic interventions (eg. glucagon, diazoxide, octreotide, corticosteroids and carnitine replacement) as well as underlying etiology of hypoglycemia and other associated diagnoses will be reviewed and collected every 2-3 days.

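### Section 8 counts blood-found and sensor-only lows under unequal rules that act differently in the two arms, so the combined count can hide, reverse or exaggerate a real effect, and recognition is not measured

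*Combined protocol and SAP*

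**What the plan says.** Section 8 (Data Analysis Plan) gives two routes to a hypoglycemic event. The blood route is any single laboratory or bedside reading under the age threshold (50 mg/dL in the first 48 hours, 70 mg/dL thereafter). The sensor route is introduced by "or CGM values below threshold for >30 minutes with no concomitant blood sugar reading". A merging rule follows: "Hypoglycemic episodes within one hour of each other will be considered as one event". On severity the plan says: "Severe hypoglycemia will be defined as less than 40mg/dL".

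Section 4c states: "The primary endpoint will be a reduction in incidence and severity of hypoglycemia in infants on the CGM Protocol". The secondary outcomes there are times to diagnosis, to treatment initiation and to euglycemia on a sustainable feeding regimen. Neither Section 4c nor Section 8 has an outcome that separates recognized from unrecognized lows.

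Under Section 4a both arms wear a sensor, masked in the Standard of Care arm. In the CGM Protocol arm an alarm or a worrying trend leads to a request for a blood glucose. Care may change only on the blood value.

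Section 1 gives the motivation: intermittent sampling "leaves infants at risk for unrecognized hypoglycemia". Section 2 cites earlier work in which, with CGMs, "hypoglycemia is detected up to 3 hours prior to the scheduled blood glucose test". The hypothesis for aim (a) is that real-time trends work by "allowing hypoglycemia to be predicted and prevented, or detected and treated before becoming severe or symptomatic".

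**The concern.** The two routes are not interchangeable, and randomization changes how often each is used. A 15-minute low counts if someone draws blood during it and does not count otherwise. The alarm causes blood to be drawn, and it works in one arm only. Conversely, a sensor run of more than 30 minutes that is merely sensor error stays an event if no blood is taken. In the CGM Protocol arm the prompted check can show a normal value and remove it. The definition therefore depends on the intervention, and the two distortions have opposite signs.

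The pooled count also discards whether anyone knew about the low. That is the problem the trial sets out to address, and the masked control sensor makes it measurable in both arms.

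At stake are the direction of the primary comparison and the event rates and variances that Sections 1 and 9 intend to carry into the larger trial.

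**Working it through.** The plan has no figure to reproduce. Section 9 sets 10 infants per arm by convention, without event rates, effect size or standard deviation. The check below applies the Section 8 rules to a single true low in each arm.

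**Inputs from the documents.** Blood route: one value, no minimum duration. Sensor route: more than 30 minutes, no concomitant blood reading (Section 8). Alarm-prompted checks in one arm only (Section 4a). Up to 12 hours between routine samples in the cited background (Section 2).

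**Assumptions.** Duration D is lognormal with median 20, 30 or 60 minutes and log-SD 0.8. Routine checks come every T = 3, 6 or 12 hours, and lows start at random within the gap. A share a = 0.8 of lows trigger the alarm. Blood is drawn 10 minutes after onset of an alarmed low. A share p of alarmed lows is prevented. The one-hour merging rule is not modelled.

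**Formulas, per true low**
- Control: S = P(D>30) + E[D; D≤30]/T. The second term is short lows that a routine check happens to hit.
- Alarmed low, not prevented: A = P(D>10) + E[D; D≤10]/T.
- CGM Protocol: C = a(1−p)A + (1−a)S.
- True ratio of lows: 1 − a·p, which is 1.00 for p = 0 and 1 − 0.8×0.3 = 0.76 for p = 0.3.

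**Worked case: median 30 minutes, T = 180 minutes**
- S = 0.500 + 8.753/180 = 0.549
- A = 0.915 + 0.615/180 = 0.919
- p = 0: C = 0.8×0.919 + 0.2×0.549 = 0.845; C/S = 1.54, true ratio 1.00
- p = 0.3: C = 0.8×0.7×0.919 + 0.2×0.549 = 0.624; C/S = 1.14, true ratio 0.76

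**Ratio of Section 8 counts, CGM Protocol to control, across T = 3 to 12 hours**

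| Median low | None prevented (true 1.00) | 30% of alarmed lows prevented (true 0.76) |
|---|---|---|
| 20 min | 1.99–2.22 | 1.45–1.61 |
| 30 min | 1.54–1.63 | 1.14–1.20 |
| 60 min | 1.15–1.17 | 0.87–0.88 |

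**Every low longer than 30 minutes, all alarmed.** The ratio is 1.00 with no prevention, 0.70 with 30% prevented and 0.50 with 50%. Here the count behaves correctly.

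**False sensor lows.** Let there be f false runs of more than 30 minutes per true low. Assume all stay counted in control and 80% are refuted in the CGM Protocol arm. The ratio is then (C + 0.2f)/(S + f).
- Worked case, p = 0: f = 0.1 gives 0.865/0.649 = 1.33; f = 0.3 gives 0.905/0.849 = 1.07.
- All true lows longer than 30 minutes, p = 0: f = 0.1 gives 1.02/1.10 = 0.93; f = 0.3 gives 1.06/1.30 = 0.82. This is an apparent benefit where there is none.

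**Recognition in the worked case, p = 0.** Runs over 30 minutes with no blood reading are 0.32 per true low in control and 0.2×0.32 = 0.06 in the CGM Protocol arm. The combined count does not isolate this contrast.

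**One sensor rule for both arms.** With runs over 30 minutes counted whether or not blood was taken, the ratio is (1 − a·p)P(D>30)/P(D>30): 1.00 for p = 0 and 0.76 for p = 0.3, at every median and T above. This assumes that prevention does not depend on duration, that treatment does not shorten a run below 30 minutes, and that there are no false runs.

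**The case against.** A reader might infer that the alarm only turns unseen lows into seen ones, so that the count is always unchanged and the pilot cannot show the effect it was built on. The documents do not support that. Aim (a) is about prevention and treatment before a low becomes severe, and the primary endpoint covers severity as well as incidence. A prevented low leaves the count, and earlier treatment can reduce values below 40 mg/dL. Checks made on the trend, on the rate-of-drop alarm, or on the 60 mg/dL alarm before 48 hours of life can precede the event threshold. The count is unchanged only if every low exceeds 30 minutes, none is prevented and none is false.

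Pooling also has a merit. In the worked case with no prevention, a blood-only count would give a ratio of 3.46 against the CGM Protocol arm, so the sensor route removes part of a larger bias. Time to diagnosis and time to treatment lie downstream of recognition, and study staff already review control traces daily for unrecognized severe lows.

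Finally, this is an unpowered feasibility study, the traces are kept, and unrecognized lows could be tabulated later. Recognition also partly reflects adherence to a check requested in one arm only.

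All of this stands, and it limits the point. It does not make the two routes equal. Section 8 does not report the daily review as an outcome and gives no definition or test for time to treatment. Because Section 1 says the pilot is meant to test the validity of its outcome measures, a definition that behaves differently by arm should be settled before the data are compared.

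**Conclusion.** The concern holds in this limited form. The Section 8 count is ascertained unequally between arms, and the bias can run either way. Over the assumed range the ratio of counts is 1.15 to 2.22 with no true difference. With a true ratio of 0.76 it is 1.14 to 1.61 at medians of 20 to 30 minutes, which reverses the benefit, and 0.87 to 0.88 at 60 minutes, which understates it. False sensor lows can lower the ratio enough to suggest a benefit where none exists. These figures rest on assumed durations, sampling gaps, alarm coverage and response time, so they show direction and range only.

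The pilot can still show prevention and reduced severity. What it lacks is a like-for-like count and any measure of recognition. This should be fixed but does not invalidate the study.

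A separate inconsistency needs the sponsor's attention. After 48 hours of life an event is defined at below 70 mg/dL (Section 8), but the level alarm sounds at below 60 mg/dL for all infants (Section 4a). Glucose is then already below the event threshold when that alarm sounds, and a low of 60 to 69 mg/dL may trigger no level alarm. The two passages must be reconciled.

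**What to change.** In Section 8:

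1. Compare the arms on one sensor-based definition applied identically to both: runs below the age threshold for more than 30 minutes, whether or not blood was taken. Add minutes below threshold and minutes below 40 mg/dL, so that lows shortened by prompt treatment still register.
2. Report the existing combined count alongside.
3. Classify each run, by arm, as blood-confirmed (a blood glucose below threshold during the run), refuted (a blood glucose at or above threshold) or unrecognized (no blood glucose). State how a run with both kinds of value is assigned.
4. Report per infant the number and minutes of unrecognized runs, and the time from run start to first blood glucose, censored at run end if none was taken. Give variances for the larger trial.

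Sensor traces and blood glucose values are already collected, so the main cost is analysis programming and a few more descriptive outcomes. There are two downsides. The comparison relies on sensor accuracy; the planned MARD addresses this and should be shown by arm, because extra blood checks may bring extra calibrations. And the recognition measure describes the detection process rather than harm avoided, so it should be labelled that way.
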